There is a risk that participants will become distressed by discussion that focuses attention in mood and engagement, will be distressed by others' shared experiences. These are always issues in therapeutic groups that are run in many NHS and other settings. Our view is that the potential benefits of the groups outweigh these risks that are mitigated to the greatest extent possible by sensitive group coordination, establishing an agreed set of rules with group members (e.g. about confidentiality) and having an agreed set of procedures for coping with distress. In this respect, for in-person and online groups, other members of the research team will be aware of when the groups are taking place and be available nearby or have a link to join an online group. Whilst it is generally better to manage distress in the group by giving the participant 'a moment' and agreeing to come back to an issue at the end of a group, if it is not possible, this proximity allows the person leading the group to get help such that the group can continue whilst a person remains 'with' the distressed individual (until the acute distress passes or other arrangements can be made). The PI on this study is a qualified clinical psychologist and the other project members have considerable experience of working with clinical groups.

The risk of a breach of confidentiality is managed by the research being conducted in accordance with best practice. Personally identifiable information ("PID" - names, addresses, dates of birth etc.) are kept strictly separate from fully anonymised research data (questionnaires, session recordings). PID are held in a secure 'haven' on our computer server and/or locked filing cabinets and will be retained for only 12 months after the last participant has completed the study (in case of a need to re-contact), after which they will be deleted. Online questionnaires will not have personally identifiable details such as the participant's name and will be collected using Qualtrics, hosted on a secure University of Cambridge-based server. All information will be transferred to the MRC CBU local server as soon as practically possible and then deleted from Qualtrics. Any participant uncomfortable with online assessments will have the option to complete the assessments over the phone or through posted questionnaires.

Another risk common to all therapeutic groups concerns breaches of confidentiality by other group members. We manage this by making it clear from the Participant Information Sheet onwards (repeated at the beginning of each group) that the participants have a responsibility to each other including confidentiality. We are explicit in asking participants not to talk about other group members outside of the group and taking no photographs or recordings. The online groups carry additional risks of service interception and from other people potentially being present in a participant's home and accidentally or intentionally seeing who is in the group or hearing what they are saying. Our understanding is that, if appropriate safeguards are taken (password protecting meetings, using 'waiting rooms', 'locking the meeting,' only allowing the host to have screen sharing and 'chat' rights) then the risk of interception is very small. To manage the risk from others in the participants' homes we ask participants in advance and at the beginning of each meeting to

- ensure that their location is as private as possible
- discuss the importance of privacy with others who may share the home

MAPLES Pilot Study for Low Mood in ABI

- shield the screen and use headphones as necessary to protect the identity of others and prevent overhearing
- make it clear to the group leader if another person is present, so that the discussion can be moderated or that participant temporarily moved to the 'waiting room' to protect others' privacy
- never to share a video-conferencing link

At the time of consent, we make participants aware that we have a duty of care that sometimes places limits on confidentiality. In in-person groups, for example, in the unlikely event that a group member had a medical emergency, we would summon relevant help (e.g. call an ambulance). We would clearly do the same thing in an online group. Similarly if participants disclose information that indicates a significant risk of harm to themselves or another person we have a responsibility to take necessary steps (such as contacting their GP or other services). All incidences such as these will be recorded and followed up as appropriate.

The groups in this trial are being offered in addition to any services normally accessed by participants. The study will not therefore deprive participants of other interventions and, potentially, of course, offers something beneficial to which they might not otherwise have access. It is possible that being offered the prospect of a therapeutic group but then having to wait some weeks before it begins would induce distress at the delay that would not otherwise have occurred. Such delays are, of course, common in clinical services and would be inevitable given the study's resources, access to rooms, need to recruit certain numbers for a group to begin etc. – it would be very rare to go straight from referral/initial assessment straight into such an intervention. We are also at pains to point out to potential participants that the reason this is research is because we do not know whether one or other intervention is of any benefit and the occurrence of delay is an important aspect of drawing meaningful scientific inference.

Participants who choose to have their contact details retained for receiving a summary of the study results and/or details about other research studies will only have their information stored on the MRC CBU secure "haven" and paper copies of contact details will be shredded after transferring details to the CBU computer server. Upon each contact beyond the MAPLES study, participants will have the option to have their contact details permanently deleted from the MRC CBU servers and not be contacted again.

Research Ethics Committee (REC) and other Regulatory review & reports

Prior to any data collection, a favourable opinion will be sought from the Cambridge Central Research Ethics Committee (REC). A detailed record will be kept of all correspondence with the REC, and annual reports will be submitted as required. Upon completion of the study, the REC will be notified immediately. The REC will additionally be notified in the case of premature termination of the trial and in the case of adverse events.

Regulatory Review & Compliance

Prior to recruitment, [name] and the research team will ensure that appropriate approvals are in place. For any amendment, the research team will in agreement with the sponsor will submit information to the appropriate REC following the appropriate timeframe.

Peer review

The MAPLES study has been independently externally reviewed by the MRC quinquennial review panel as part of the overall research programme directed by [name]. The MRC quinquennial review panel consists of experts within psychology as well as experts outside of psychology that are both UK based and international. The trial, as part of the larger research programme, has received positive feedback from the MRC based on its overall value and impact.

Patient & Public Involvement

MAPLES Pilot Study for Low Mood in ABI

The MAPLES study has and will continue to benefit from the invaluable input of service users. Eleven individuals with an acquired brain injury and four caregivers were interviewed about typical barriers and facilitators of engagement in day-to-day and enjoyable activities. Interview participants were also asked to provide feedback on the content covered within the Activity Planning group and whether they found the topics useful. Notable feedback from participants includes 1) the importance of managing fatigue and 2) the perceived importance of practising social engagement skills. The Activity Planning group now emphasises fatigue management in relation to planning and engaging in activities, as well as roleplay to practice skills related to engaging and communicating with others. The current content in the Activity Planning group has also been modified to remove discussion around self-rewards (e.g., a cup of tea for every increase in activity) and generating alternative solutions (i.e., back up plans for activities). Participants felt that self-rewards and generating alternative solutions for all activities would be unmanageable in the long-term and thus could affect long-term outcome in the MAPLES study. The results from these interviews have been essential in ensuring that the proposed treatment has face validity with individuals with an ABI and their caregivers.

Secondly, the MAPLES study steering committee will include a service user of CCS. We have consulted with an occupational therapist based within CCS to recommend a suitable service user to be part of the steering committee. Along with their insight into how to enhance acceptability of the trial (i.e., ways to prevent attrition), they will be involved in the dissemination of the research. The service user on our steering committee will be of great aid in helping ensure our research is accessible to clients with an ABI.

Continual patient and public involvement is not only important in trial management but from those participating in the research as well. The MAPLES study will therefore benefit from conducting exit interviews with all participants in order to enhance acceptability of a future full scale trial.

Protocol compliance

Protocol compliance will be managed primarily by review of recruitment strategies, intervention delivery, and assessment administration during the steering committee meetings. Members of our steering committee and NHS staff involved in recruitment will be able to provide feedback on method of recruitment. Regular review of documentation of evidence of eligibility will be conducted by a member of the MRC CBU research team not conducting the screening process nor conducting the intervention.

All group sessions will be audio-recorded in order to code the sessions for intervention fidelity. This will help ensure protocol compliance. Assessment session compliance (i.e., completing the full questionnaire battery) will be done by using a checklist and comment section to input any information as to why an assessment was completed only in part (i.e., severe participant fatigue).

Any protocol deviations, whether accidental or intentional, will be documented and reported to the Chief Investigator and Sponsor immediately. Immediate action will be taken to resolve non-compliance.

Data protection and patient confidentiality

Paperwork and files relating to study participants will be stored in locked filing cabinets at the MRC Cognition and Brain Sciences Unit, only accessible by the research team. Personally identifiable data and anonymised data will be stored separately in order to decrease the risk of breaches to confidentiality. Only the research team will have access to personal information (contact details) for the purposes of contacting participants. The research team will only access medical records once for the purposes of collecting injury-related information. Medical information will not be stored with participant contact information and will only be linked to anonymised participant indicators. The

MAPLES Pilot Study for Low Mood in ABI

research data (questionnaires, administered in person, by post, or online) will only contain anonymised participant indicators.

The first type of information transferring between NHS records and the research team will be contact details for participants who have expressed an interest in potentially taking part/hearing more about the study (i.e. who have consented for the NHS clinician to pass this information on). This will typically be conveyed to the research team in a phone call. We will ask clinicians not to use email and delete any such email (after writing down the details) should it be sent. On receiving the phone call the researcher will write down the details and keep them in a locked filing cabinet at the CBU – a secured building with strict guidelines on visitors arriving via reception and being accompanied in movements around the building. The researcher will also make an electronic record which will be retained only in space within the CBU's secure computing area to which the MAPLES research team have access. If contact details are given to the researcher in person whilst at an NHS site, these will be listed on a separate piece of paper (i.e. not in a note book or diary) or recorded on an encrypted laptop and returned to the CBU as soon as is possible. Here they will be locked in the filing cabinet/transferred to the secure computing area and then deleted from the laptop.

For participants recruited from non-NHS ABI charities, participant contact details will only be retained for the purposes of the research study once they have agreed to it via the Invitation Letter or by sending an email confirming that they agree for their contact details to be retained. Participants recruited through the CCNRP will be re-reminded that their contact details and information are currently retained by the CBU and will be given the opportunity for their details to be removed from the participant panel. Other than this small difference in accessing contact information, the same data storage and protection and policy will be the same as described above for all participants.

If participants do not consent to take part or withdraw from the study, paper and electronic contact details will be immediately deleted from our records.

Once consent is given we will allocate a unique participant number to an individual. There will be an electronic and paper version of the key linking names with participant numbers. Only the participant number and never the name or date of birth etc. will be used on all other documents and electronic records (questionnaires, tests, clinical information etc.) in the study.

The researcher will have a copy of the key on an encrypted, strong password protected USB drive during her visits to NHS sites, non-NHS ABI charities, or participants' homes so that she can, by opening it in a laptop, allocate the correct number to any documents (test scoresheets, questionnaires etc.). The encrypted USB drive will have no information other than the key (i.e. that might give context to what the key was) and no external labels linking it to the study. The key will never be copied to the laptop. Any electronic information relating to participants will be stored on the encrypted laptop, that, during transit, will be carried separately from the encrypted USB drive. Similarly, any questionnaires, scoresheets etc. carried from NHS sites or homes back to the CBU will have only a participant number. If there is consent for the researcher to view medical records, she will make written electronic notes of details pertinent to characterising a participant's neurological impairment. No scans or photocopies of medical notes will be made and only the participant number will be used to identify the electronic record. No details that could uniquely identify an individual (e.g. unusual occupation) will be recorded. Clinical notes would never be removed from the NHS site.

On returning to the CBU, all such anonymous electronic records will be transferred from the laptop to the CBU servers and then deleted from the laptop. Anonymous paper records will be electronically scanned with the files being stored on CBU servers in addition to the paper records being retained in a locked filing cabinet for the duration of the study (in the long term only electronic versions will be stored). The USB key will be kept in the locked filing cabinet between NHS/home visits.

MAPLES Pilot Study for Low Mood in ABI

In the above manner, if the encrypted USB drive was lost or stolen it is extremely unlikely that the strong password could be guessed. Even if it was, the only information available would be a list of names and numbers which would have little meaning outside of the study context. Similarly, if the laptop was stolen and the encryption bypassed, or paper records lost or stolen, there would only be clinical details, questionnaire scores etc. that could not be linked to any individual. The data will be analysed at the MRC Cognition and Brain Sciences Unit. Analysis will primarily be conducted by [name] with input from [name], [name], [name], and [name], the statistician at the MRC Cognition and Brain Sciences Unit. All data that is analysed will be fully anonymised and will be stored in an encrypted computer.

Only anonymised data will be kept in the long-term, stored locally within the MRC Cognition and Brain Sciences Unit. The MRC recommends that trial data is stored for at least 20 years post-completion of the trial. However, there is increasing emphasis on making fully anonymised data 'open' for scientific review and such that other research questions could be addressed by researchers around the world – indeed it is now a condition of publication in some journals. When data are made open, in principle they are preserved indefinitely. Hence, the data will be stored as open access files online indefinitely. [name] will serve as the data custodian.

Access to the final study dataset

Only [name] and [name] will have access to any dataset that has personally identifiable information, although at 12 months post-trial completion all personally identifiable information will be permanently deleted. Prior to uploading the fully anonymised final dataset as described above, only members of the research team will have access to the full dataset. In the participant information sheet, it is explained that data may be reanalysed for a separate analysis or as part of a larger study.

REFERENCES

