Here, we will investigate the benefits of BA primarily in people who have sustained traumatic brain injuries (TBI) and, for the first time in ABI, examine the efficacy of group rather than individual therapy. There are clear economic advantages to group, compared with individual, therapy and, when they work well, the supportive dynamics of groups of people with similar challenges can enhance therapeutic effects. It might be expected that conventional BA, in which people learn about the importance of activity engagement, of scheduling activities in everyday life and of overcoming barriers and resisting avoidant behaviour would lead to more generalised and lasting gains than simply engaging in rewarding activities without such knowledge and skill acquisition. However, it is also possible that cognitive problems (e.g. in remembering details) may undermine these gains. Accordingly, we will compare this conventional BA group ("activity planning") with a second intervention group ("activity engagement") in which participants will be encouraged to engage in potentially rewarding activities (crafts, games, social discussion) but which will not emphasise planning and scheduling activities outside of the group. Here it is possible that, through positive experiences of engagement, participants implicitly or explicitly generalise to increase activity levels in daily life. This second intervention also serves to make it clearer, should the "activity planning" be associated with

MAPLES Pilot Study for Low Mood in ABI

greater gains in activity and mood that it is likely attributable to the conventional BA component rather than more general group dynamics.

Cognitive impairments in ABI such as inability to override habits in favour of new behaviours may pose barriers to BA's success. Incorporating cognitive training developed specifically for ABI may enhance the effectiveness of BA. For example, Goal Management Training (GMT; (Levine et al., 2000, 2011) is designed to help individuals with ABI overcome habits, generate solutions, and attain goals. GMT is well-suited to groups, with participants providing support and feedback to one another, alongside "homework" designed to encourage understanding and application of skills (Levine et al., 2011).

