Hence, reducing the impact of cognitive impairments in ABI may contribute to improvements in mood alongside BA. Therefore, the proposed study will investigate the feasibility and acceptability of two ABI-specific BA interventions, and whether one or other intervention is superior in improving mood and activity levels and how each compares to participants assessed and re-assessed on the outcome measures over the same period but with no intervention other than care as usual (waitlist condition)

Objectives

The primary objective of the MAPLES study is to determine the feasibility of two Behavioural Activation group interventions in individuals with an acquired brain injury (ABI) with low mood. This will be based on participant retention from baseline to 1-month post-intervention, acceptability of the proposed skills in the group sessions and assessments, and participant feedback from the exit interview. The two behavioural activation groups will be administered both in person and online.

A secondary objective of the MAPLES study is to evaluate whether training adults with an acquired brain injury to plan and engage in meaningful, valued, and/or enjoyable activities has detectable effects on activity level and mood compared to a waitlist control condition.

Hypotheses

There are no specific hypotheses related to the level of acceptability and feasibility of the trial whether in person or online.

Study Groups

- 1) Activity Planning Group – BA Intervention arm
- 2) Activity Engagement Group – the social group
- 3) Waitlist Group

HA-1: Relative to participants in the Waitlist Group, participants in the Activity Planning and Activity Engagement Groups will have greater increases in activity level from pre- to post-intervention and at 1 month post-intervention.

H0-1: There will be no differences in activity level from pre- to post-intervention and at 1 month post-intervention across all groups.

HA-2: Relative to participants in the Waitlist Group, participants in the Activity Planning and Activity Engagement Groups will have greater improvements in mood from pre- to post-intervention and at 1 month post-intervention.

H0-2: There will be no differences in mood from pre- to post-intervention and at 1 month post-intervention across all groups

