The COVID-19 pandemic has meant that we have had to suspend all in-person contact with research participants. In the current substantial amendment, we are proposing to continue the study using only telephone and on-line contact with participants. Whilst this was not part of our original plan, it does

MAPLES Pilot Study for Low Mood in ABI

offer an opportunity to examine the relative feasibility and acceptability of in-person vs. online videoconferencing groups. This is useful both during the pandemic, whilst social distancing restrictions remain in place, and also afterwards when new means of tele-therapy may have value for patients (e.g. those that find it difficult to travel) and services.

STUDY DESIGN and METHODS of DATA COLLECTION AND DATA ANALYSIS

Trial Design

Activity Planning Group

Generally, those receiving BA training develop and maintain a schedule based on activities that have been enjoyable, pleasant, meaningful, or interesting in the past (Mazzuchelli et al., 2010). Clients are then instructed to monitor their daily mood and participation in these activities to identify the connection between them. Clients are then taught how to increase the frequency and quality of positive events and decrease negative ones (Lewinsohn, 1976; Lewinsohn et al., 1980). In GMT, participants learn how to identify precursors to becoming distracted from their goals and strategies to orient themselves to their environment in order to prevent goal neglect (Levine et al., 2000, 2011).

The intervention will consist of weekly 1 hour group sessions over the course of 8 weeks, covering 8 overarching themes:

- 1) Introduction to Group Therapy
- 2) Identifying Enjoyable Activities
- 3) The Automatic Pilot and Planning Pleasurable Activities
- 4) Goal Review and Balancing Enjoyable and Routine Activities
- 5) Identifying Solutions to Goal Neglect
- 6) Increasing Mastery and Managing Fatigue
- 7) Active Approaches to Engagement
- 8) Relapse Prevention

All sessions will be administered by [name]. Although we have received feedback from individuals with an ABI on the content covered within the Activity Planning Group, if participants within the MAPLES study react negatively to the content covered within the program then such content will be removed from the intervention or restructured so as to not potentially cause distress for future participants.

Activity Engagement Group

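### The Activity Planning arm combines behavioural activation with Goal Management Training, so an advantage over Activity Engagement supports the package, not conventional BA alone

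*Combined protocol and SAP*

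**What the plan says.** Background and Rationale describes the first group as "conventional BA, in which people learn about the importance of activity engagement, of scheduling activities in everyday life and of overcoming barriers", together with resisting avoidance. It gives the second group two purposes. One is to see whether rewarding activity within sessions carries over to daily life. The other is to help with interpretation: if the Planning group is associated with "greater gains in activity and mood that it is likely attributable to the conventional BA component rather than more general group dynamics", the second group is meant to make that clearer.

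The next paragraph introduces GMT as something added: "Incorporating cognitive training developed specifically for ABI may enhance the effectiveness of BA". The section then concludes: "Hence, reducing the impact of cognitive impairments in ABI may contribute to improvements in mood alongside BA".

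Under Trial Design, the Activity Planning Group text describes BA and then GMT: "In GMT, participants learn how to identify precursors to becoming distracted from their goals and strategies to orient themselves to their environment". Goal neglect is the fifth of the eight session themes. Patient & Public Involvement adds an emphasis on managing fatigue, "as well as roleplay to practice skills related to engaging and communicating with others".

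The Activity Engagement Group text lists eight social sessions (games, crafts, puzzles, a quiz) without therapeutic goals. GMT is not mentioned there, nor in the description of the online version. Study Groups labels arm 1 simply as the BA intervention arm.

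**The concern.** The protocol defines conventional BA in one paragraph, adds a second ingredient in the next, and says that this ingredient may act on the same outcome. It then gives both ingredients to one arm and neither to the active comparator. The sentence on attribution names only the first.

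The comparison will be read. The end of the Background asks whether one intervention is superior to the other, and the Analysis section predicts that Planning will do better than Engagement. If it does, a reader following the rationale would conclude that conventional BA works in groups after brain injury. The result would be equally compatible with a benefit from GMT, or from the two together. The protocol looks ahead to a full-scale trial, and the choice of what to carry into it could rest on that reading.

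**Working it through.** The plan gives no sample size, effect size or standard deviation on this point, so there is no figure to reproduce. The check asks what the three arms can identify.

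**Inputs**
- Activity Planning: 8 weekly group sessions of 1 hour, with BA and GMT (Activity Planning Group; Background and Rationale).
- Activity Engagement: 8 weekly group sessions of 1 hour, social activities, no BA or GMT described (Activity Engagement Group).
- Waitlist: usual care only over the same period.
- Planned analysis: a general linear model on the BADS across assessments, with no analysis by component (Analysis).

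**Contact time.** 8 × 1 = 8 hours in each group arm, so scheduled contact is equal.

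**Expected change by arm.** Let u be the change under usual care, g the effect of group contact and activity, b the effect of BA and m the effect of GMT, taken as additive.
- Waitlist = u
- Engagement = u + g
- Planning = u + g + b + m

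**Contrasts**
- Engagement − Waitlist = g. Estimable.
- Planning − Engagement = b + m. Estimable as a sum.
- b alone: not estimable. The columns for b and m are identical (1 in Planning, 0 elsewhere), so the design matrix has rank 3 for 4 unknowns.

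**Fuller coding.** Giving fatigue management and role-play their own terms yields 6 unknowns for 3 arms. The rank is still 3. BA alone is again not estimable, and the sum of everything specific to Planning is.

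**Illustration only.** A hypothetical fourth arm with group contact and BA but no GMT raises the rank to 4 and makes b estimable. The obstacle is therefore which conditions are compared. The number of participants does not enter the calculation.

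**Could another planned feature separate them?** Re-randomisation after the waitlist places people in the same two groups. The online versions are meant to resemble the in-person ones. Neither creates a condition with BA but not GMT.

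**The case against.** The strongest reply is that the sentence claims little. It is hedged twice: the second group makes matters clearer, and the gain is likely attributable. Its stated contrast is with group dynamics, which matched contact supports. It sits in the background and is not a reporting rule. The secondary objective and both numbered hypotheses compare with waitlist. The GMT content is disclosed in the next paragraph and again under Trial Design, so no reader is told that the arm is unmodified BA.

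Much of this stands. The group-dynamics half of the sentence is right and should be kept. The plan does not commit the final report to crediting BA, and attribution is not the comparator's only purpose. But the hedge does not rescue the other half: nothing in the design makes BA a likelier source than GMT. Disclosure sharpens the difficulty, because the protocol itself names GMT as a possible second cause.

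Two stronger readings are tempting, and the documents do not support them.
- A reader might treat fatigue management and role-play as further non-BA ingredients on a par with GMT. The plan's own account of BA includes overcoming barriers, it ties fatigue management to planning and engaging in activities, and role-play can be read in the same way. They are weaker examples, and the point does not need them.
- A reader might count session titles and infer that a large part of the programme is not BA. Only the goal-neglect theme, 1 of 8, is explicitly linked to GMT by the text. Other titles are mixed or unexplained, and counting titles does not measure content or effect.

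**Conclusion.** The point holds for GMT. The design supports attributing a Planning advantage over Engagement to the Activity Planning package rather than to general group contact. It does not support attributing that advantage to conventional BA.

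No numerical share can be given to either component. The documents supply no information on the split, and the trial will not generate any.

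The conclusion rests on two readings of the text: that GMT is distinct from conventional BA, as the protocol's own definition and its language of addition imply, and that the Engagement group does not receive GMT, since none is described. Additivity was assumed for simplicity. If GMT strengthens BA, as the protocol suggests it may, an interaction term adds a further unknown and separation becomes harder still.

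This is a fault in a stated inference. Recruitment, allocation, the outcome measures and the primary feasibility conclusions are unaffected.

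**What to change.** 1. In Background and Rationale, replace the attribution sentence with wording such as: *If Activity Planning shows larger gains than Activity Engagement, the difference will be attributed to the combined Activity Planning package (BA with GMT), over and above general group contact. The separate contributions of BA and GMT cannot be distinguished in this design.*
2. In Study Groups, relabel arm 1 as BA with GMT.

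The cost is a text change and a narrower claim. No arm, participant, assessment or analysis is added.

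Protocol compliance already provides for audio recordings to be coded for fidelity. Recording BA and GMT content separately there would be a useful description of what was delivered, but it is optional and does not solve the attribution problem, because both components are given to the same people.
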